## 1.2 SCHEMA

## 1.3 SCHEDULE OF ACTIVITIES (SOA)

Procedures	Enrollment/ Baseline Study day 1	Daily visits throughout hospitalization	Hospital Discharge	1-month post- hospitalization +/- 7 days	3-months post- hospitalization +/- 14 days	12-months post- hospitalization EMR review
Informed consent	X					
Demographics	X					
Medical history	X					
Randomization	X					
Administer study intervention	X					
Vital signs- (BP, HR, RR, O2 sat)	X					
Height	X					
Weight	X		X			
Pregnancy test if needed	X					
Anemia labs a	X	X	X	X	X	
Platelet count d	X		X			
White blood cell count d	X		X			
Creatinine d	X		X			
Functional outcome assessment b	X		X	X	X	
Con medication review c	X	X				
Fluid balance	X		X			
RBC transfusions documented	X	X	X	X	X	
Daily phlebotomies for labs (excluding RMGs)		X	X			
Fatigue assessment			X	X	X	
AE review and evaluation	X	X	X	X	X	
Research Samples e	X			X	X	
Hospital readmissions documentation				X	X	X
All cause mortality status						X
Complete Case Report Forms	X	X	X	X	X	X

a. Hemoglobin, ferritin, and transferrin saturation will be obtained for all patients at enrollment, hospital discharge, 1-month, and 3-months post-hospitalization. Other anemia labs to be reported at these and other timepoints include, if available Hemoglobin, MCV, RDW, ferritin, iron, transferrin saturation, reticulocyte hemoglobin, absolute reticulocyte count; record all values available recognizing that not all non-hemoglobin values will be available at each interval.

b. Functional outcomes according to the Core Outcome Measurement Set will be obtained in the following fashion: Enrollment – ADL survey (by patient or proxy); at Hospital discharge – EQ-5D, PROMIS-FATIGUE; at 1-month and 3-months – EQ-5D, PROMIS-FATIGUE, 6MWD, ADL Survey, MoCA-BLIND, HADS, IES-R, activity monitoring (optional study component).

c. Concomitant meds review to include y/n for antiplatelet agents (i.e. aspirin, clopidogrel), anticoagulants (i.e. heparin, warfarin, direct oral anticoagulants, low molecular weight heparins), iron, and erythropoiesis stimulating agent use (i.e. darbepoetin, EPO). Daily visits only need to report if they received iron or EPO/darbepoetin.

d. Platelets, WBC and Creatinine will be collected if done as standard of care. Baseline results used should be from within 24 hrs prior to enrollment. Hospital discharge results used should be the closest to discharge up to 72 hours prior.

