#### 4.4 END OF STUDY DEFINITION

A participant is considered to have completed the study if they have completed all phases of the study including the last visit shown in the Schedule of Activities (SoA), Section 1.3. Data on mortality and hospital readmission will be extracted at 12-months post-hospitalization for each patient by review of the electronic medical record.

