## 8.2 SAFETY AND OTHER ASSESSMENTS

Subjects will undergo the following procedures/evaluations:

- **Vital signs.** Temperature, pulse, respirations, blood pressure, continuous telemetry, oxygen saturations will be monitored during administration of iron and EPO for those in the intervention group as outlined in section 2.3. All subjects will receive standard ICU monitoring throughout their stay in the ICU.
- **Weight.** Subjects < 40 kg will be excluded due to unclear safety of 40,000 unit of EPO in persons with low weights
- **Assessment of adverse events.** Medical records will be reviewed daily for evaluation of adverse events. Adverse events will be indicated on the data forms for the study and on the specific adverse event report forms and all serious adverse events will be reported to the IRB within 24 hours of the research team learning about the event followed by a more detailed written report to the IRB. The following information about adverse events will be collected: 1) the onset and resolution of the event, 2) an assessment of the severity or intensity of the event, 3) an assessment of the relationship of the event to the intervention, and 4) any action taken because of event. The PI will report all potentially related SAEs to the DSMB and to NHLBI within 7 days of discovery.

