#### 8.3.4 TIME PERIOD AND FREQUENCY FOR EVENT ASSESSMENT AND FOLLOW-UP

The occurrence of an adverse event (AE) or serious adverse event (SAE) may come to the attention of study personnel during study visits and interviews of a study participant presenting for medical care, or upon review by a study monitor.

As noted earlier, for this study we plan to observe for a specific set of AEs and this information will be captured on the appropriate case report form (CRF). Information to be collected includes event description, time of onset, clinician’s assessment of severity, relationship to study product (assessed only by those with the training and authority to make a diagnosis), and time of resolution/stabilization of the event. All AEs will be followed to adequate resolution.

Changes in the severity of an AE will be documented to allow an assessment of the duration of the event at each level of severity to be performed.

Study coordinators will record all listed reportable events with start dates occurring any time after informed consent is obtained through 3-months after hospitalization. At each study visit, the investigator will inquire about the occurrence of AE/SAEs since the last visit. Events will be followed for outcome information until resolution or stabilization.

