#### 9.4.4 SAFETY ANALYSES

All AEs and SAEs will be presented and compared between groups. Mortality and hospital readmission rates will also be presented and compared between groups.

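### After discharge, adverse events and transfusions have scheduled capture only at the 1- and 3-month visits, and the safety comparison makes no allowance for incomplete follow-up or death

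*Combined protocol and SAP*

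**What the plan says.** **Window.** Section 8.3.4: "Study coordinators will record all listed reportable events with start dates occurring any time after informed consent is obtained through 3-months after hospitalization". The window therefore includes the hospital stay, so its length varies by participant.

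**Routes of capture.** Section 8.2: "Medical records will be reviewed daily for evaluation of adverse events". No end date is given. Section 8.3.4 adds: "At each study visit, the investigator will inquire about the occurrence of AE/SAEs since the last visit". It also says that events may come to attention "during study visits and interviews of a study participant presenting for medical care, or upon review by a study monitor".

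**Schedule.** In section 1.3 the row "AE review and evaluation" is marked at baseline, daily throughout hospitalization, at discharge, and at 1 and 3 months. The RBC transfusion row has the same marks. Neither is marked at the 12-month electronic record review, whose content section 4.4 gives as: "Data on mortality and hospital readmission will be extracted at 12-months post-hospitalization".

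**Analysis.** For adverse events section 9.4.4 says: "All AEs and SAEs will be presented and compared between groups". For mortality and readmission, section 9.4.3 specifies cumulative incidence, censoring at last known contact with the health system, and log-rank and Gray's tests. RBC units are an endpoint in section 3 and transfusion rates are to be compared according to section 4.1, but transfusions are not in the 9.4.3 endpoint list and have no named estimator.

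**The concern.** The intensity of scheduled observation falls at discharge, and from then on it depends on attendance. The listed events in section 8.3.1 include venous thromboembolism, myocardial infarction and non-hemorrhagic stroke. Section 2.3.1 names thrombosis, infarction and stroke among the risks of EPO and says that existing critical-care data do not exclude a clinically significant increase in adverse events. The 3-month window shows that post-discharge events are meant to count.

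If 9.4.4 is carried out as counts or proportions over all randomized, a non-attender with an unrecorded event looks the same as a participant without one. A participant who dies early looks the same as one followed to 3 months. The bundle is expected to affect survival and readmission (section 2.3.2), and clinicians and participants know the allocation (section 6.3), so observed time could differ by arm. The safety data are meant to inform a phase III trial (section 9.4.9), so absolute risks matter as well as the contrast.

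**Working it through.** **1. Scheduled capture, from section 1.3.**

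| Item | Baseline and daily in hospital | Discharge | 1 month | 3 months | 12-month record review |
|---|---|---|---|---|---|
| Adverse events | yes | yes | yes | yes | no |
| RBC transfusions | yes | yes | yes | yes | no |
| Readmissions | no | no | yes | yes | yes |
| All-cause mortality | no | no | no | no | yes |

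Someone discharged alive who attends neither visit has no scheduled source for the first two rows after discharge.

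**2. How many could be affected.** Inputs: 74 evaluable, 100 enrolled, up to 25% lost through death or loss to follow-up (9.2), and up to 10% ICU mortality (9.4.2).

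- The plan's enrollment figure reproduces: 74 / 0.75 = 98.7, so 99. By arm, 37 / 0.75 = 49.3, so 50, or 100 in total.
- Taking both ceilings: 100 × 0.25 = 25 without a 1-month value and 100 × 0.10 = 10 ICU deaths. That leaves 25 − 10 = 15 of 100 − 10 = 90 ICU survivors, or 17%.
- This counts participants without a 1-month hemoglobin, not those who miss both visits. It includes later deaths, and it includes people who attend at 3 months, when the enquiry looks back to the last visit. The group with no scheduled capture is probably smaller.
- The 15 rests on both ceilings holding together. With 5 ICU deaths and the same total, it would be 20 of 95, again including later deaths.

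**3. Mechanism, on assumed inputs.** The documents give no adverse event rate, no length of stay and no attendance by arm, so what follows shows direction only. Let *m* be the share with no capture after discharge by any route, *R* the true risk over the window, and *L* the days in hospital after enrollment, followed by 90 days. Assume a constant hazard and no deaths.

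- *h* = −ln(1 − *R*) / (*L* + 90); in-hospital risk *p* = 1 − exp(−*hL*); recorded risk = (1 − *m*)*R* + *mp*.
- Equal non-capture. With *R* = 10%, *L* = 10 and *m* = 25% in both arms: *h* = 0.00105, *p* = 0.0105, recorded risk = 0.75 × 0.10 + 0.25 × 0.0105 = 7.8%. Over *L* = 5 to 30 days it is 7.6% to 8.2%. This *m* is deliberately severe, as it treats the whole planned loss as never captured. With no true effect, the risk ratio stays at 1.
- Unequal non-capture, no true effect. With *m* = 20% against 30%, *R* = 10% and *L* = 10: 0.0821 / 0.0731 = 1.12. Over *R* = 5% to 20% and *L* = 5 to 30 it is 1.09 to 1.13. With 15% against 35% it is 1.20 to 1.28.
- If half of the events occur in hospital: (0.80 + 0.20 × 0.5) / (0.70 + 0.30 × 0.5) = 0.90 / 0.85 = 1.06, and for 15% against 35%, 0.925 / 0.825 = 1.12.
- Stay alone, with full capture and the same hazard. At 10 against 15 days the windows are 100 and 105 days, and the risk ratio is 1.04 to 1.05.

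**The case against.** Four stronger readings are tempting, and the documents do not support them.

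- **Events are captured only at attended visits.** Section 8.3.4 gives coordinators a recording duty through 3 months that does not depend on attendance, and it allows capture when a participant presents for care or on monitor review. Section 8.2 puts no end date on record review, although the daily column in section 1.3 is confined to hospitalization. Participants belong to the local or regional health system (5.1, 5.5), missed visits trigger repeated contact attempts (7.3), and readmissions are documented. The gap is therefore in scheduled capture.
- **The plan counts unobserved time as event-free.** Section 9.4.4 names no estimator. That outcome follows only if simple counts or proportions over all randomized are used, which the text neither requires nor prevents.
- **A given percentage of events will be missed.** That would need the 15 to be alive, never seen and invisible to every other route, plus an assumed share of events after discharge.
- **The arms are compared with bias.** Equal non-capture mainly lowers both absolute risks. No figure in the documents shows attendance, death or stay differing by arm.

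Two further points are fair. Section 10.1.6 defers safety oversight to a Data and Safety Monitoring Plan that is not among these documents, and it may say more about ascertainment. Also, in a 100-patient pilot with few events, proportions reported alongside follow-up would be defensible. Both limit the weight of the point. Neither settles what is recorded for a discharged non-attender, nor how 9.4.4 treats death. Starting the window at consent is trivial, since consent and randomization share study day 1.

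**Conclusion.** The point holds as a gap in scheduled ascertainment together with an underspecified safety analysis. A discharged participant who attends neither visit has no scheduled capture of listed events or transfusions, and 9.4.4 lacks the handling of follow-up that 9.4.3 gives to mortality and readmission.

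On the plan's ceilings about 15 of 90 ICU survivors could be affected, probably fewer. Under simple proportions the likely effect is understated absolute risk. A distorted contrast needs a difference between arms in attendance, death or stay, and the ratios in the working rest on assumed rates, stays and attendance. The primary hemoglobin analysis is untouched. This is an inexpensive improvement, not a demonstrated bias.

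**What to change.** 1. **Ascertainment (1.3, 4.4, 8.2, 8.3.4).** Extend the planned electronic record review to the listed adverse events and RBC units, with onset dates, through 3 months post-hospitalization. Do this for every randomized participant who has not withdrawn permission for record review, regardless of visit attendance and with the same abstraction in both arms. State whether the daily record review in 8.2 ends at discharge.
2. **Analysis (9.4.4).** Report adverse events from randomization as cumulative incidence, censored at last ascertainment, with death as a competing event, in line with 9.4.3. Report observed follow-up by arm.
3. **Window.** Keep the protocol's 3-months-post-hospitalization window for adverse events and RBC units. A fixed window from randomization, such as day 90, is an optional sensitivity analysis and should not replace it: with a 28-day stay the planned window is 28 + 90 = 118 days, so a day-90 cut would discard the last 28.

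The cost is modest extra abstraction time in a chart review already planned, plus a few sentences in the analysis section. Onset is already a recorded item. Care received outside the health system would remain uncaptured.

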#### 9.4.5 BASELINE DESCRIPTIVE STATISTICS

Descriptive statistics will be utilized to present baseline demographic, clinical, and laboratory features for both groups. No inferential statistics will be utilized.

#### 9.4.6 PLANNED INTERIM ANALYSES

Not applicable

#### 9.4.7 SUB-GROUP ANALYSES

We do not expect treatment effect heterogeneity of this intervention. However, exploratory analyses will assess potential for heterogeneity of treatment effect using interaction analyses in LMM models for the primary endpoint. An interaction term between randomized arm and each of sex, age, anemic etiology, and surgical vs. medical admissions, will be evaluated separately. The estimate of the treatment effect will be reported in subgroups using linear contrasts of with the interaction analysis when evidence supports a statistically significant interaction.

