Briefly, this is a randomized clinical trial of a multifaceted anemia prevention and treatment bundle versus standard of care to assess the impact of the intervention on hemoglobin recovery and post-hospitalization functional outcomes. Each patient randomized to the intervention will receive 3 treatment components: 1) optimized phlebotomy practice; 2) clinical decision support; and 3) pharmacologic anemia treatment. With regards to pharmacologic anemia treatment, patients may receive either a single dose of intravenous (IV) iron therapy in isolation if they have an iron-responsive anemia or a single dose of EPO if they have an anemia of inflammation requiring erythropoietic stimulation. Further, some patients receiving EPO may also receive a single dose of IV iron to replenish iron stores prior to EPO administration

(i.e. if serum ferritin is < 1000 ng/ml at the time of randomization). Patients randomized to the standard of care arm will receive usual ICU cares.

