Patients satisfying inclusion/exclusion criteria, or their legal proxies, will be approached by trained study coordinators for written informed consent. Participants will be randomized 1:1 to active intervention vs. standard care using a stratified permuted block design by anemia etiology (iron-responsive or not) and ICU admission indication (surgical vs. non-surgical). The intervention arm is multi-faceted with 3 primary components: 1) **Optimized phlebotomy**, defined by minimal volume draws (i.e. 0.1-2 ml vs. standard 3-10 ml per laboratory order) and closed-loop blood sampling (eliminates 10 ml waste volume per draw), all performed by a dedicated phlebotomy team independent from the treatment team; 2) **Decision support aids**, including visual and electronic alerts reminding the care team to minimize non-essential laboratory testing and mitigate patient-specific bleeding risk (e.g. stress ulcer prophylaxis in high-risk patients); and 3) **Pharmacologic anemia treatment** (given immediately following enrollment when hemoglobin first observed <10 g/dL) targeted to 2 broad groups: 1) anemias responsive to iron supplementation alone (i.e. acute blood loss, true iron deficiency [i.e. ferritin <100 ng/ml, transferrin saturation < 20%]), and 2) anemias requiring erythropoietic stimulation (e.g. anemia of inflammation, anemia of renal disease). Etiology of anemia will be determined immediately prior to randomization upon review of laboratory values (i.e. iron studies) and clinical history (i.e. admission diagnoses, surgery/acute blood loss) with treatment decisions adjudicated pre-randomization by the PI or Co-I's. Subjects then randomized to the intervention arm will receive pharmacologic anemia treatment in accordance with their anemia etiology. Patients with anemias responsive to iron supplementation will receive a single total dose infusion (1000 mg) of intravenous (IV) iron dextran. Patients with anemias requiring erythropoietic stimulation will receive a single dose of 40,000 units of subcutaneous EPO, which will be immediately preceded by 1000 mg of IV iron dextran to replenish usable iron stores if the ferritin level is < 1000 ng/ml. All patients randomized to the intervention group will receive

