either IV iron, EPO, or both. Targeted pharmacologic anemia therapies are being employed given that anemia in acute blood loss/post-surgery and true iron deficiency is iron-restricted and responds to iron supplementation alone; hence, the potential harms of EPO (e.g. thrombosis) likely outweigh benefits.

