## 6 STUDY INTERVENTION

### 6.1 STUDY INTERVENTION(S) ADMINISTRATION

#### 6.1.1 STUDY INTERVENTION DESCRIPTION

The intervention arm is multi-faceted with 3 primary components:

- 1) **Optimized phlebotomy**, defined by minimal volume draws (i.e. 0.1-2 ml vs. standard 3-10 ml per laboratory order) and closed-loop blood sampling, all performed by a dedicated phlebotomy team independent from the treatment team. This intervention simply requires communication with the phlebotomy team rather than any direct change to patient care.
- 2) **Decision support**. This includes:
  - a. A visual clinical support tool (appendix) urging the clinical team to minimize laboratory assessments and optimize patient bleeding risk. This will be available by the clinical workstations for the ICU team and at the patient's bedside.
  - b. A daily rounding checklist (appendix) accompanied by brief daily discussion (2-minutes) between trained study coordinators and the ICU care team during clinical rounds to reiterate the purpose of the study. The checklist will be available at the clinical workstations for the ICU team.
  - c. Epic direct messages sent twice per day (targeting day and night providers) with the information from the visual support tool to reiterate the purpose of the study.
- 3) **Pharmacologic anemia treatment**. These therapies will be given immediately following enrollment and targeted to 2 broad groups:
  - a. Anemias responsive to iron supplementation alone. This includes patients with anemia secondary to acute blood loss  $\geq$  500 ml and patients with iron deficiency anemia (i.e. ferritin  $<100$  ng/ml or transferrin saturation  $<20\%$ ).
    - Patients with iron-responsive anemias will receive a single total dose infusion (1000 mg) of intravenous (IV) low molecular weight iron dextran (INFeD)
    - This medication is diluted in 500 ml of 0.9% saline. A 25 mg test dose (12.5 ml) is administered over 5 minutes to ensure no immediate hypersensitivity reaction, followed by the completion of the infusion over 1-2 hours (not to exceed 1000 mg/hr). This medication will be given in accordance with Mayo Clinic administration guidelines.

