  - b. Anemias requiring erythropoietic stimulation. This includes anemia not secondary to acute blood loss or iron deficiency (e.g. anemia of inflammation, anemia of renal disease). Etiology will be determined immediately *prior to randomization* upon review of laboratory values (i.e. iron studies) and clinical history (i.e. admission diagnoses, surgery/acute blood loss) with treatment decisions adjudicated pre-randomization by the PI and trial Co-I's should the PI be unavailable.
    - Patients without iron-responsive anemias will receive a single dose of 40,000 units of subcutaneous EPO (Retacrit). For those with ferritin less than 1000 ng/ml they will also receive 1000 mg IV iron prior to EPO administration to replenish usable iron, given that iron will

invariably be mobilized secondary to EPO stimulation. EPO will be given in accordance with Mayo Clinic administration guidelines.

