### 6.3 MEASURES TO MINIMIZE BIAS: RANDOMIZATION AND BLINDING

Participants will be randomized 1:1 to active intervention vs. standard of care using a stratified permuted block design by anemia etiology (iron responsive vs. not) and ICU admission indication (surgical vs. non-surgical). Randomization will occur electronically using the REDCap randomization module. Randomization lists will be developed by the study statisticians and uploaded directly to REDCap. Study staff involved in patient care are unable to access randomization lists in advance and therefore are unlikely to predict future randomization/assignment. Clinicians and subjects will not be blinded to study interventions. However, all data analysts will be blinded to treatment allocation while the study is ongoing.

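### Section 9.4.7 promises treatment effects by anemia etiology, which decides the drug given, only when the interaction test is significant; they should be reported unconditionally as descriptive estimates

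*Combined protocol and SAP*

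**What the plan says.** Section 9.4.7 (Sub-Group Analyses) expects no heterogeneity but plans exploratory interaction tests for the primary endpoint, within the linear mixed model (LMM): "An interaction term between randomized arm and each of sex, age, anemic etiology, and surgical vs. medical admissions, will be evaluated separately". Subgroup effects will then be "reported in subgroups using linear contrasts of with the interaction analysis when evidence supports a statistically significant interaction". The section gives no significance level for the interaction and does not say at which visit, or over which visits, it is evaluated.

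Etiology has a larger role than the other three factors:

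- Section 4.1: "Subjects then randomized to the intervention arm will receive pharmacologic anemia treatment in accordance with their anemia etiology".
- Section 6.1.1, iron-responsive group: "Patients with iron-responsive anemias will receive a single total dose infusion" of IV iron. The other group receives EPO, and "For those with ferritin less than 1000 ng/ml they will also receive 1000 mg IV iron prior to EPO administration".
- Section 6.3: randomization uses a "stratified permuted block design by anemia etiology (iron responsive vs. not) and ICU admission indication (surgical vs. non-surgical").

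The targeting rests on a premise stated in section 4.1, that "anemia in acute blood loss/post-surgery and true iron deficiency is iron-restricted and responds to iron supplementation alone". Section 4.2 calls the trial a pilot for a larger definitive trial, and section 9.4.9 says the exploratory analyses are to inform a multicenter phase III trial. Apart from these uses, etiology enters the analysis as an adjustment covariate in section 9.4.2. No section plans a treatment effect by etiology outside the rule in 9.4.7.

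**The concern.** The two etiology strata receive different drug regimens, so how the bundle performed in each is something the designers of the next trial would want to know. Making those estimates depend on a significant interaction in a trial of about 75 evaluable patients has two consequences. Real but moderate heterogeneity will usually fail the test, and the planned report then contains neither the stratum effects nor their uncertainty. When the test is passed, the contrast has been selected for being large and overstates the truth on average.

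There is a related gap in wording. The model has four visits and an arm-by-time interaction (section 9.4.2), but section 9.4.7 names only an arm-by-factor term. That could mean the contrast at 1 month or an average over visits. The 1-month reading is plausible, because 9.4.7 refers to the primary endpoint and 9.4.2 makes 1 month primary. The two readings have different precision.

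**Working it through.** **Inputs from the plan.** Section 9.2 gives a 1-month SD of 1.5 g/dL; R² = 0.25 for the adjustment variables, so the residual SD is 1.5 × √0.75 = 1.30; 100 enrolled; and up to 25% dropout, leaving 75. Allocation is 1:1 within strata (section 6.3). Two-sided alpha of 0.05 is taken from section 9.4.3, which sets it for secondary and exploratory outcomes.

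**Assumptions, not in the documents.** Etiology split from 50:50 to 80:20; between-visit correlation ρ from 0.3 to 0.7; true stratum differences of 1.0 and 2.0 g/dL.

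**The plan's own figures reproduce.** For 1.0 g/dL with SD 1.5 and 37 per group, the noncentral t gives 80.8% power (stated: 80%). With SD 1.30 it gives 90.4% (stated: 90%). Inflating 74 for 25% dropout gives 74 / 0.75 = 98.7, so 99 (stated: 100).

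**Interaction at 1 month.** With n₁ and n₂ evaluable patients in the two strata:

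SE = SD × √(4/n₁ + 4/n₂)

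The smallest significant observed difference is 1.96 × SE. For example, with N = 75, 50:50 and SD 1.30, SE = 1.30 × √(4/37.5 + 4/37.5) = 0.600 and the threshold is 1.18. Power is two-sided normal. The mean absolute estimate given significance comes from the truncated normal.

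| N = 75 | SE | Threshold (g/dL) | Power, true 1.0 | Mean if significant, true 1.0 | Mean if significant, true 2.0 |
|---|---|---|---|---|---|
| SD 1.30, 50:50 | 0.600 | 1.18 | 38% | 1.60 | 2.10 |
| SD 1.30, 80:20 | 0.750 | 1.47 | 27% | 1.93 | 2.31 |
| SD 1.50, 50:50 | 0.693 | 1.36 | 30% | 1.80 | 2.22 |
| SD 1.50, 80:20 | 0.866 | 1.70 | 21% | 2.19 | 2.51 |

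Every threshold exceeds the 1.0 g/dL effect for which the trial is powered. With a true difference of 1.0 g/dL, the test is not passed in 62% to 79% of trials. With a true difference of 2.0 g/dL, power is about 64% to 92% and the inflation is much smaller. With no dropout (N = 100), thresholds are 1.02 to 1.47, power at 1.0 g/dL is 27% to 49%, and the mean significant difference is 1.4 to 1.9.

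**Interaction averaged over four visits.** With equal variances and the same N at each visit, the SE is multiplied by √((1 + 3ρ)/4), which is 0.689, 0.791 and 0.880 for ρ = 0.3, 0.5 and 0.7.

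- N = 75: threshold 0.81 to 1.49; power at 1.0 g/dL 26% to 68%.
- N = 100: threshold 0.70 to 1.29; power at 1.0 g/dL 33% to 80%.

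On this reading the threshold can fall below 1.0 g/dL.

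**Precision if the estimates were always reported.** The 1-month 95% half-width in a stratum is 1.96 × SD × √(4/n). At N = 75 this is ±0.83 to ±0.96 g/dL per stratum at 50:50. At 80:20 it is ±0.66 to ±0.76 in the larger stratum and ±1.31 to ±1.52 in the smaller one, which would hold about 15 patients.

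**The case against.** The rule can be defended as conservative. The analyses are labelled exploratory, no heterogeneity is expected, four factors are tested without multiplicity adjustment, and holding back small-subgroup estimates limits over-reading. The text says *when*, not *only when*, the interaction is significant, and reporting the interaction estimate with its CI is neither barred nor promised. The trial team will hold the data and can compute the stratum effects in any case.

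The estimates also have limits. "Each patient randomized to the intervention will receive 3 treatment components", so a stratum effect is that of the whole bundle. It cannot isolate iron or EPO, or show whether EPO would add anything in the iron-responsive group. The contrast between strata is not randomized and is tied to surgery and blood loss. The numbers depend on an assumed split, and a difference of 1.0 g/dL equals the entire planned main effect. The upper threshold of 1.70 uses the unadjusted SD; with the adjusted SD the range is 1.18 to 1.47.

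Much of this stands. This is an improvement to the plan, not an error in it; the estimates would be descriptive; and the figures hold only under the stated assumptions. The conservative argument itself does not hold: selecting results by significance passes on the extreme ones, whereas an interval reported regardless shows how little is known. A prespecified estimate is also stronger than one the team decides to compute later. That no heterogeneity is expected is an assumption, and a non-significant test with 21% to 38% power at a true difference of 1.0 g/dL gives it little support.

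**Conclusion.** The concern holds, as an inexpensive improvement that should be made. On the 1-month reading with 75 evaluable patients, the rule releases etiology-specific effects only if the strata differ by more than about 1.2 to 1.7 g/dL. It would withhold them in 62% to 79% of trials when the true difference is 1.0 g/dL, and the differences that passed would average 1.6 to 2.2 g/dL.

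This rests on the SDs in section 9.2, alpha of 0.05 borrowed from section 9.4.3, and the assumed split of 50:50 to 80:20. The conclusion is weaker if dropout is lower or if the interaction is averaged over visits, where power can reach 80%. If there is no heterogeneity little is lost, because the overall estimate serves both strata. The primary analysis is not affected.

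**What to change.** Add to section 9.4.7:

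> The 1-month treatment effect with 95% CI in each anemia-etiology stratum (iron-responsive; not iron-responsive), and the interaction estimate with 95% CI, will be reported regardless of the interaction p-value, from a model with arm × time × etiology and all lower-order terms, evaluated at 1 month. These are descriptive effects of the whole bundle versus usual care within each etiology group, not isolated effects of iron or EPO.

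This also settles which etiology interaction is tested. The significance condition may stay for sex, age and surgical versus medical admission. Surgical admission is a randomization stratum too, but it does not itself set the drug; it enters through the etiology classification. The two factors may therefore overlap, and the report should say so.

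The cost is the two sentences above, a line on that overlap, and three table rows (two strata and the interaction), with no new data or patients. The drawback is wide intervals, up to about ±1.5 g/dL in a 20% stratum, which could be over-read unless the rows are clearly labelled descriptive.
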